11. REGULATORY AND REPORTING REQUIREMENTS

This study involves exposure to radiation and is appropriate for Human Use Subcommittee Review. FDG-PET is a clinically approved procedure for patients with cancer. However, for this research study, FDG is being performed under IND# 113,858 and [¹⁸F]Flutemetamol is being performed under IND#109,760 ([name] is IND holder for both INDs), as such the following FDA reporting of unexpected fatal or life threatening events, serious adverse events, and serious and unexpected adverse events will occur: (1) reporting any unexpected fatal or life threatening adverse experience associated with the use of [¹⁸F]Flutemetamol by telephone or fax no later than 7 calendar days after initial receipt of the information. (2) Reporting any adverse experience associated with the use of [¹⁸F]Flutemetamol, that is both serious (SAE) and unexpected in writing

no later than 15 calendar days after initial receipt of the information. (3) Submitting annual reports. The reportable events will also be submitted to the IRB using the University of Utah ERICA online system:

<https://erica.research.utah.edu/erica/Rooms/DisplayPages/LayoutInitial?Container=com.webridge.entity.Entity%5B0ID%5B5FD2DA60262617429607E459C0E09D92%5D%5D>

The descriptions and grading scales found in the revised NCI Common Terminology Criteria for Adverse Events (CTCAE) version 4.03 will be utilized for adverse event reporting (<http://ctep.cancer.gov/reporting/index.html>).

All appropriate research areas will have access to a copy of the CTCAE version 4.03 with modifications. A list of adverse events that have occurred or might occur (Reported Adverse Events and Potential Risks) can be found in Section 6 (Imaging Studies Information).

The reportable events will also be submitted to the IRB using the University of Utah ERICA online system:

<https://erica.research.utah.edu/erica/Rooms/DisplayPages/LayoutInitial?Container=com.webridge.entity.Entity%5B0ID%5B5FD2DA60262617429607E459C0E09D92%5D%5D>

Adverse events will be assessed for [¹⁸F]Flutemetamol immediately following the imaging scan. Additionally, a follow-up telephone call will be made to each participant within 1 day following their imaging scan. If the participant cannot be contacted at 1 day post-scanning, then we will continue trying to contact them for up to 7 days post-scanning.

11.1 Expedited Adverse Event Reporting

Those adverse events which are not associated with [¹⁸F]Flutemetamol do not require expedited reporting and will be reported in the routine manner to the IRB. Adverse event reporting is only required for events within 24 hours from the time of the injection of the experimental imaging agents [¹⁸F]Flutemetamol.

11.2 Expedited Reporting Guidelines – Phase 1/2 studies with Investigational Agents

The guidelines given in **Table 5** below will be followed. Any unexpected fatal or life threatening adverse experience associated with the use of [¹⁸F]Flutemetamol will be reported to the FDA by telephone or fax no later than 7 calendar days after initial receipt of the information. All reportable adverse events will be submitted to the FDA & IRB within the required timeframe by as mandated by the FDA and IRB. Hospitalization will be defined as any medical event equivalent to CTCAE grade 3, 4, or 5 that precipitated hospitalization (or prolongation of existing hospitalization).

Adverse event reporting is only required for events within 24 hours from the time of the injection of the experimental imaging agent [¹⁸F]Flutemetamol.

Table 5.

UNEXPECTED EVENT		EXPECTED EVENT	
GRADES 3 Attribution of Possible, Probable or Definite	GRADES 4 and 5 Regardless of Attribution	GRADES 1 - 3	GRADES 4 and 5 Regardless of Attribution
Expedited report within 10 working days. (Grade 1 or 2 Adverse Event Expedited Reporting NOT required.) Report to FDA Report to HCI DSMC	Expedited report to follow within 7 working days. Any late death attributed to the agent (possible, probable, or definite) should be reported within 7 working days. Report to FDA Report to HCI DSMC	Adverse Event Expedited Reporting NOT required.	Expedited report within 7 working days. Any late death attributed to the agent (possible, probable, or definite) should be reported within 7 working days. Report to FDA Report to HCI DSMC

For **Hospitalization** only – Any medical event equivalent to CTCAE grade 3, 4, or 5 that precipitated hospitalization (or prolongation of existing hospitalization) must be reported regardless of designation as expected or unexpected and attribution.

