APPENDIX I: GE Healthcare Supplemental Safety Reporting Form

SUPPLEMENTAL SAFETY CRF

IS& ID	SUBJECT NO.	GEHC MDx Product:
[]	[]	[]

Effective Date: 21-Feb-2013

Date of Birth	Gender (check one)
[]	 Male  Female
D D M M M M	 White  Black or African American
Y Y Y Y Y Y	 Hispanic or Latino  Not Hispanic or Latino
	1 2
	3 4
	5 6
	7 8
	9 10
	11 12
	13 14
	15 16
	17 18
	19 20
	21 22
	23 24
	25 26
	27 28
	29 30
	31 32
	33 34
	35 36
	37 38
	39 40
	41 42
	43 44
	45 46
	47 48
	49 50
	51 52
	53 54
	55 56
	57 58
	59 60
	61 62
	63 64
	65 66
	67 68
	69 70
	71 72
	73 74
	75 76
	77 78
	79 80
	81 82
	83 84
	85 86
	87 88
	89 90
	91 92
	93 94
	95 96
	97 98
	99 100

PRE-TREATMENT EVENTS AND TREATMENT-EMERGENT EVENTS

Record AEs outcomes or attribution to agent. Serious AEs should be reported to GE within 24hrs using the SAE form provided in your ISS Site Manual.

Event No.	Event (Record diagnosis in Standard Medical Terminology) (Record One Event Per Line) Be as specific as possible, for example: Infection = NOT SPECIFIC Upper respiratory infection = SPECIFIC	Date / Time of Dose Administration	Date / Time of Onset	Date / Time of Resolution	Intensity	Relationship to IMP	Treatment Given	Action Taken With Study Treatment	Outcome of Adverse Event			
									1=Yes** 2=No	1=Not Related 2=Related	1=Resolved 2=Not Resolved 3=Fatal 4=Unknown	1=Yes** 2=No
1.												
2.												
3.												

**If treatment given, specify:

D D M M M M	Y Y Y Y Y Y
[]	[]
H H	M M

D D M M M M	Y Y Y Y Y Y
[]	[]
H H	M M

D D M M M M	Y Y Y Y Y Y
[]	[]
H H	M M

**If treatment given, specify:

D D M M M M	Y Y Y Y Y Y
[]	[]
H H	M M

D D M M M M	Y Y Y Y Y Y
[]	[]
H H	M M

**If treatment given, specify:

D D M M M M	Y Y Y Y Y Y
[]	[]
H H	M M

Date: [] [] [] [] [] []

Primary Investigator/Designee's Signature: _____

SAE defined as: Any event that resulted in death, was immediately life-threatening, required inpatient hospitalization or prolongation of existing hospitalization, resulted in persistent or significant disability or incapacity, was a congenital anomaly or birth defect, or required medical or surgical intervention to prevent one of the outcomes listed above.

Significant events which when based on appropriate medical judgment may jeopardize the subject and may require medical/surgical intervention to prevent one of the outcomes listed above.

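### Section 11.2 and Table 5 sort expedited reports by CTCAE grade, Section 11 item (2) by seriousness; the two conflict for serious, unexpected grade 1-2 events

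*Combined protocol and SAP*

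**What the plan says.** Section 11.2 states that the guidelines in Table 5 will be followed. Those guidelines sort events by expectedness, CTCAE grade and, for unexpected grade 3 events, attribution. On admissions, the section says "Hospitalization will be defined as any medical event equivalent to CTCAE grade 3, 4, or 5 that precipitated hospitalization" (or prolonged an existing stay). In the unexpected-event part of Table 5 it adds "Grade 1 or 2 Adverse Event Expedited Reporting NOT required". A note under the table says that an admission caused by a grade 3, 4 or 5 event "must be reported regardless of designation as expected or unexpected and attribution". The note widens reporting across expectedness and attribution but keeps the grade limit. Table 5 names two recipients, the FDA and the HCI DSMC.

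Section 11 item (2) uses a different trigger. It covers any adverse experience associated with flutemetamol "that is both serious (SAE) and unexpected in writing", to be sent to the FDA "no later than 15 calendar days after initial receipt of the information". It sets no grade condition.

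Section 11 does not define serious. Appendix I, the GE Healthcare supplemental safety form, does: "SAE defined as: Any event that resulted in death, was immediately life-threatening, required inpatient hospitalization or prolongation of existing hospitalization", followed by disability, congenital anomaly, and intervention to prevent such outcomes. The same form says "Serious AEs should be reported to GE within 24hrs using the SAE form".

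Section 11.4 has the DSMC review all SAEs. Sections 11.1 and 11.2 limit adverse event reporting to the 24 hours after the flutemetamol injection.

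**The concern.** Seriousness describes the outcome of an event and grade describes its severity. The protocol uses seriousness to set its FDA duty in Section 11 and grade to set its working triage rule in Section 11.2. An event can be low in grade and still serious, for example if the patient is admitted for observation. For such an event the two sections give opposite instructions.

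Staff who look in Section 11 and its subsections for the meaning of hospitalization find only the grade-limited version. The outcome-based definition is several appendices away, on a manufacturer's form. If they sort the event by Table 5, they may conclude that no expedited report is due, although Section 11 item (2) requires one. In a trial this small, safety oversight rests on single events, so one that is missed or late matters.

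**Working it through.** No computed figure is involved. The check is to apply each rule to one test event and compare the results.

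**Test event.** An unexpected, flutemetamol-associated event of CTCAE grade 2, with onset within 24 hours of injection, that leads to inpatient admission.

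| Rule | Trigger | Result for the test event |
|---|---|---|
| Section 11 item (2), with the Appendix I definition | Serious and unexpected, any grade | Written FDA report within 15 calendar days |
| Appendix I | Any SAE | Report to GE within 24 hours |
| Section 11.4 | Any SAE | DSMC review |
| Section 11.2 definition of hospitalization | Grade 3-5 only | Not a hospitalization |
| Table 5, unexpected events | Grade 3-5 | Expedited report not required |
| Note under Table 5 | Grade 3-5 admission | Does not apply |

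The first and fifth rows contradict each other. The sixth does not resolve the contradiction, because the note carries the same grade limit.

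**Variations on the test event.**

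1. *Grade 1-2, unexpected, serious on another Appendix I criterion (for example, intervention to prevent a listed outcome).* The result is the same: due under Section 11 item (2), exempt under Table 5.
2. *Grade 3-5, unexpected, associated with the agent.* Table 5 requires an expedited report, and the note catches any admission. The two rules agree that a report is due.
3. *Grade 1-2, expected, with admission.* Table 5 exempts it, and Section 11 item (2) does not apply because the event is not unexpected. There is no conflict over the FDA report. The GE report and DSMC review still apply.

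The conflict is therefore confined to events that are grade 1-2, serious, unexpected, associated with flutemetamol, and within the 24-hour window.

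**Does other text settle which rule prevails?** Sections 11.2 and 11.3 both say that reportable events go to the FDA and IRB on the mandated timeframe, but they do not say which events are reportable, and that is the question. Section 11.3 lists no exclusions from expedited reporting. Its heading refers to expected events, however, and Table 5 itself exempts expected grades 1-3, so 11.3 does not settle the matter. No sentence ranks Section 11 above Table 5 or the reverse.

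**Exposure.** Up to 15 participants × 1 flutemetamol injection = at most 15 injections, each with a 24-hour reporting window.

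**The case against.** The strongest reply is that nothing is lost on paper. Table 5 waives only expedited reporting under that table. Section 11 item (2) remains in force with no grade condition, as do the general submission clause, the GE report and DSMC review of all SAEs. A reader might infer from Table 5 that serious grade 1-2 events go unreported altogether. The documents do not support that: the duties exist, and the fault is that another instruction contradicts one of them.

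A reader might also infer that the GE deadline is waived. It is not. Table 5 never mentions GE, so it cannot remove the 24-hour report in Appendix I. Any risk to that report is indirect and arises only if the event is not recognised as serious. Nor can one say that Section 11 itself classes the test event as serious, because it uses the term without defining it.

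Two further points have weight. The note under Table 5 mainly adds reporting, since it brings in admissions that expectedness or attribution would otherwise exempt. And the SAE form in Appendix H records intensity (mild, moderate, severe) separately from the seriousness criteria, with hospitalization as its own box, so anyone completing that form would be prompted to think about outcome. But the SAE form is reached only after someone has judged the event serious, and Section 11.2 is the place where that judgement is likely to go wrong. The separate fields also show that the protocol's own paperwork foresees a mild or moderate event with admission, which the Section 11.2 definition excludes.

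Finally, CTCAE 4.03 is only linked in Appendix F. Whether a particular reaction would still be graded 2 once the patient is admitted cannot be checked from the documents. If every serious event were graded 3 or higher, the conflict would never arise in practice. In that case, though, the grade condition on hospitalization would serve no purpose.

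**Conclusion.** The conflict is real and narrow. For a serious, unexpected, flutemetamol-associated event of grade 1-2 within 24 hours of injection, Section 11 item (2) requires an FDA report within 15 calendar days, Section 11.2 and Table 5 say that no expedited report is needed, and nothing decides between them. The consequence is a risk that the expedited FDA report, or the DSMC's notice of the event, is missed or late. It is not a plan under which such events are never reported.

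The number of events will be small. The documents give no rate for this class. The ALZ103 study in Section 4.2.3, with 22 evaluable subjects given the ¹⁸F agent, reports no SAE during the study. With at most 15 injections here, the count may well be zero.

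The conclusion assumes that the Appendix I definition is the one Section 11 intends, since no other is given, and that a grade 1-2 event can meet a seriousness criterion. It has no bearing on the endpoint, sample size or analysis. The wording should still be corrected, because a triage rule that the protocol says will be followed gives a result contrary to the protocol's own FDA duty.

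**What to change.** Make four changes of wording:

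1. Put one outcome-based definition of serious, using the Appendix I criteria, in Section 11.
2. Remove the grade condition from the definition of hospitalization in Section 11.2 and from the note under Table 5.
3. Limit the grade 1-2 exemption in Table 5 to non-serious events.
4. State that Section 11 items (1) and (2) govern any serious, unexpected, flutemetamol-associated event whatever its CTCAE grade.

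The cost is a protocol amendment to Section 11 and Section 11.2 with its table, and an occasional extra expedited report. No procedure, visit or participant is added.

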11.3 Expedited Expected Adverse Event Reporting Exclusions

For this protocol, the following adverse events are specifically excluded from expedited AE reporting: **None**

Note: All deaths on study will be reported using expedited reporting regardless of causality. Attribution to treatment or other cause will be provided.

Fatal and life-threatening events will be reported to the IRB within 24 hours of notification of the event, indicating that a full report will follow. Any unexpected fatal or life threatening adverse experience associated with the use of [¹⁸F]Flutemetamol will be reported to the FDA by telephone or fax no later than 7 calendar days after initial receipt of the information. All reportable adverse

events will be submitted to the FDA & IRB within the required timeframe by as mandated by the FDA and IRB.

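### For unexpected fatal or life-threatening events associated with flutemetamol, Table 5 allows 7 working days to report to the FDA, while sections 11, 11.2 and 11.3 require notice within 7 calendar days

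*Combined protocol and SAP*

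**What the plan says.** Section 11.2 gives its table binding force: "The guidelines given in Table 5 below will be followed".

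For unexpected events of grades 4 and 5, regardless of attribution, Table 5 states "Expedited report to follow within 7 working days". The same cell adds: "Any late death attributed to the agent (possible, probable, or definite) should be reported within 7 working days". It ends with the recipients, "Report to FDA Report to HCI DSMC". The cell for expected grade 4 and 5 events gives the same period ("Expedited report within 7 working days"), the same late-death sentence and the same recipients.

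The sentence of section 11.2 that comes straight after the instruction to follow Table 5 sets a different clock. Unexpected fatal or life-threatening experiences associated with flutemetamol go to the FDA "by telephone or fax no later than 7 calendar days after initial receipt of the information". Section 11 sets the same limit in its item (1) ("no later than 7 calendar days after initial receipt of the information"), and section 11.3 repeats it. Item (2) of section 11 separately requires a written report of serious and unexpected events within 15 calendar days.

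Section 11.3 also has a clock for another recipient: "Fatal and life-threatening events will be reported to the IRB within 24 hours of notification of the event".

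**The concern.** One section gives two FDA deadlines for an overlapping set of events, in different units, with no rule of precedence. The sentence in sections 11.2 and 11.3 that reportable events will be submitted in the timeframe mandated by the FDA and IRB contains no number, so it does not settle the matter.

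Study staff are likely to work from the table. It has no telephone or fax step and no limit in calendar days. Someone who used its full allowance for an unexpected, agent-associated fatal or life-threatening event would comply with Table 5 and breach the deadline that the text states three times. What is at stake is the timeliness of the most serious safety notices.

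**Working it through.** The plan has no figure of its own to reproduce here, so the check is one of scope and one of calendar conversion.

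**Scope.** The text rule applies when three conditions hold together: the event is unexpected, it is fatal or life-threatening, and it is associated with flutemetamol. I assume that fatal and life-threatening events fall in grades 4 and 5; the protocol does not spell out this mapping. Set against Table 5:

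- Unexpected grade 4-5 cell: overlaps the text rule for events associated with the agent. Events in this cell that are not associated with it carry no 7-calendar-day duty.
- Late-death sentence: overlaps the text rule where the death is unexpected. It is already limited to deaths attributed to the agent, and it does not depend on the grade mapping.
- Expected grade 4-5 cell: no overlap for expected events.
- Unexpected grade 3 cell (10 working days) and expected grade 1-3 cell (no expedited report): no overlap under the same mapping.

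**Conversion.** Inputs are 7 working days (Table 5) and 7 calendar days (sections 11, 11.2 and 11.3). I assume a Monday-to-Friday working week without holidays. For each weekday of receipt, let C be the number of calendar days from receipt to the seventh working day. The excess over the text limit is C − 7.

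| Day of receipt | C, counting from the day after receipt | Excess | C, weekday of receipt counted as day 1 | Excess |
|---|---|---|---|---|
| Monday | 9 | 2 | 8 | 1 |
| Tuesday | 9 | 2 | 8 | 1 |
| Wednesday | 9 | 2 | 8 | 1 |
| Thursday | 11 | 4 | 8 | 1 |
| Friday | 11 | 4 | 10 | 3 |
| Saturday | 10 | 3 | 10 | 3 |
| Sunday | 9 | 2 | 9 | 2 |

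Two examples under the first convention. For receipt on Monday, the working days are Tuesday to Friday (4) and the next Monday to Wednesday (3), so C = 9. For receipt on Thursday, they are Friday (1), the next Monday to Friday (5) and the Monday after that (1), so C = 11.

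The table's limit is later than the text's limit for every day of receipt under either convention. A public holiday on a weekday within the period widens the gap.

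**Check on the written-report reading.** If Table 5 were the schedule for a written report, its periods would have to fit within the 15 calendar days of section 11. Under the first convention, 7 working days is 9 to 11 calendar days and 10 working days is 12 to 14. Both fit, holidays aside.

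**The case against.** The strongest reply is that the two clocks are cumulative. The text states the earlier limit directly above the table, and nothing says that the table displaces it. Meeting the earlier duty meets both. On this view Table 5 is the written-report schedule. Its first sentence speaks of a report to follow, section 11.3 uses the same two-step pattern for the IRB, and the periods fit the 15-calendar-day written limit.

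Part of this stands. The table sets an outer limit, and a report made early under it can still meet 7 calendar days. The written-report reading is also a fair way to reconcile the first sentence of the cell. It does not cover the late-death sentence, which says that such deaths should be reported within 7 working days, has no wording about a follow-up, and is followed by the instruction to report to the FDA. An unexpected death attributed to the agent falls squarely under the 7-calendar-day rule. Nor does the table label itself as a schedule for written reports.

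A reader might also infer that the missing 24-hour IRB notice is a second contradiction. It is not: Table 5 names only the FDA and the HCI DSMC, and the IRB notice is a separate duty to another recipient.

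**Conclusion.** The inconsistency is real and narrow. It concerns unexpected fatal or life-threatening events associated with flutemetamol, including unexpected deaths attributed to the agent. For these, the table's outer limit is 2 to 4 days past the text's limit, or 1 to 3 days if a weekday of receipt counts as day 1. These figures assume a Monday-to-Friday week and no holidays.

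Two stronger readings are tempting and unsupported. One is that staff who follow the table will report late; the documents show only that the table permits it. The other is that all grade 4-5 reporting in Table 5 conflicts with the text; expected events and events not associated with the agent lie outside the 7-calendar-day rule.

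This is a safety-reporting inconsistency and not a design choice. It does not touch the endpoint, the analysis or the sample size. Such events may be few, since section 11.4 classes the trial as low risk and enrolment is at most about 15. It should still be corrected, because the rule governs the most serious events and the correction is cheap.

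**What to change.** Reconcile the unexpected grade 4-5 cell of Table 5, including its late-death sentence, with sections 11, 11.2 and 11.3. For unexpected fatal or life-threatening events associated with flutemetamol, the cell should show the first FDA notice by telephone or fax within 7 calendar days. Any later date should be labelled as the written follow-up report.

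A cross-reference to the 24-hour IRB notice in section 11.3 would help the user of the table but is optional. The conflict gives no reason to convert the other cells to calendar days.

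The cost is the wording of one table cell in the next amendment. No data collection or analysis changes.
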